8.4.1.1. Reporting SAEs to Pfizer Safety

All SAEs occurring in a participant during the active collection period as described in [Section 8.4.1](#) are reported to Pfizer Safety on the CT SAE Report Form immediately upon awareness and under no circumstance should this exceed 24 hours, as indicated in [Appendix 3](#), [Section 10.3](#). The investigator will submit any updated SAE data to the sponsor within 24 hours of its being available.

8.4.1.2. Recording Nonserious AEs and SAEs on the CRF

All nonserious AEs and SAEs occurring in a participant during the active collection period, which begins after obtaining informed consent as described in [Section 8.4.1](#), will be recorded on the AE section of the CRF.

The investigator is to record on the CRF all directly observed and all spontaneously reported AEs and SAEs reported by the participant.

As part of ongoing safety reviews conducted by the sponsor, any nonserious AE that is determined by the sponsor to be serious will be reported by the sponsor as an SAE. To assist in the determination of case seriousness, further information may be requested from the investigator to provide clarity and understanding of the event in the context of the clinical study.

8.4.2. Method of Detecting AEs and SAEs

The method of recording, evaluating, and assessing causality of AEs and SAEs and the procedures for completing and transmitting SAE reports are provided in [Appendix 3](#), [Section 10.3](#).

Care will be taken not to introduce bias when detecting AEs and/or SAEs. Open-ended and nonleading verbal questioning of the participant is the preferred method to inquire about AE occurrences.

8.4.3. Follow-Up of AEs and SAEs

After the initial AE or SAE report, the investigator is required to proactively follow each participant at subsequent visits/contacts. For each event, the investigator must pursue and obtain adequate information until resolution, stabilization, the event is otherwise explained, or the participant is lost to follow-up (as defined in [Section 7.3](#)).

In general, follow-up information will include a description of the event in sufficient detail to allow for a complete medical assessment of the case and independent determination of possible causality. Any information relevant to the event, such as concomitant medications and illnesses, must be provided. In the case of a participant death, a summary of available autopsy findings must be submitted as soon as possible to Pfizer Safety.

Further information on follow-up procedures is provided in [Appendix 3, Section 10.3](#).

8.4.4. Regulatory Reporting Requirements for SAEs

Prompt notification by the investigator to the sponsor of an SAE is essential so that legal obligations and ethical responsibilities toward the safety of participants and the safety of a study intervention under clinical investigation are met.

The sponsor has a legal responsibility to notify both the local regulatory authority and other regulatory agencies about the safety of a study intervention under clinical investigation. The sponsor will comply with country-specific regulatory requirements relating to safety reporting to the regulatory authority, IRBs/ECs, and investigators.

Investigator safety reports must be prepared for SUSARs according to local regulatory requirements and sponsor policy and forwarded to investigators as necessary.

An investigator who receives SUSARs or other specific safety information (eg, summary or listing of SAEs) from the sponsor will review and then file it along with the SRSD(s) for the study and will notify the IRB/EC, if appropriate according to local requirements.

8.4.5. Environmental Exposure, Exposure During Pregnancy or Breastfeeding, and Occupational Exposure

Environmental exposure occurs when a person not enrolled in the study as a participant receives unplanned direct contact with or exposure to the study intervention. Such exposure may or may not lead to the occurrence of an AE or SAE. Persons at risk for environmental exposure include healthcare providers, family members, and others who may be exposed. An environmental exposure may include EDP, EDB, and occupational exposure.

Any such exposures to the study intervention under study are reportable to Pfizer Safety within 24 hours of investigator awareness.

8.4.5.1. Exposure During Pregnancy

An EDP occurs if:

- A female participant is found to be pregnant while receiving or after discontinuing study intervention.
- A male participant who is receiving or has discontinued study intervention inseminates a female partner.
- A female nonparticipant is found to be pregnant while being exposed or having been exposed to study intervention because of environmental exposure. Below are examples of environmental EDP:
 - A female family member or healthcare provider reports that she is pregnant after having been exposed to the study intervention by ingestion, inhalation, or skin contact, etc.

- A male family member or healthcare provider who has been exposed to the study intervention by ingestion, inhalation, or skin contact then inseminates his female partner prior to or around the time of conception.

The investigator must report EDP to Pfizer Safety within 24 hours of the investigator's awareness, irrespective of whether an SAE has occurred. The initial information submitted should include the anticipated date of delivery (see below for information related to termination of pregnancy).

- If EDP occurs in a participant/participant's partner, the investigator must report this information to Pfizer Safety on the CT SAE Report Form and an EDP Supplemental Form, regardless of whether an SAE has occurred. Details of the pregnancy will be collected after the start of study intervention and until at least 5 terminal half-lives after the last dose or until study end for devices, whichever is longer.
- If EDP occurs in the setting of environmental exposure, the investigator must report information to Pfizer Safety using the CT SAE Report Form and EDP Supplemental Form. Since the exposure information does not pertain to the participant enrolled in the study, the information is not recorded on a CRF; however, a copy of the completed CT SAE Report Form is maintained in the investigator site file.

Follow-up is conducted to obtain general information on the pregnancy and its outcome for all EDP reports with an unknown outcome. The investigator will follow the pregnancy until completion (or until pregnancy termination) and notify Pfizer Safety of the outcome as a follow-up to the initial EDP Supplemental Form. In the case of a live birth, the structural integrity of the neonate can be assessed at the time of birth. In the event of a termination, the reason(s) for termination should be specified and, if clinically possible, the structural integrity of the terminated fetus should be assessed by gross visual inspection (unless preprocedure test findings are conclusive for a congenital anomaly and the findings are reported).

Abnormal pregnancy outcomes are considered SAEs. If the outcome of the pregnancy meets the criteria for an SAE (ie, ectopic pregnancy, spontaneous abortion, intrauterine fetal demise, neonatal death, or congenital anomaly in a live-born baby, a terminated fetus, an intrauterine fetal demise, or a neonatal death), the investigator should follow the procedures for reporting SAEs. Additional information about pregnancy outcomes that are reported to Pfizer Safety as SAEs follows:

- Spontaneous abortion including miscarriage and missed abortion should be reported as an SAE;
- Neonatal deaths that occur within 1 month of birth should be reported, without regard to causality, as SAEs. In addition, infant deaths after 1 month should be reported as SAEs when the investigator assesses the infant death as related or possibly related to exposure to the study intervention.

Additional information regarding the EDP may be requested by the sponsor. Further follow-up of birth outcomes will be handled on a case-by-case basis (eg, follow-up on preterm infants to identify developmental delays). In the case of paternal exposure, the investigator will provide the participant with the Pregnant Partner Release of Information Form to deliver to his partner. The investigator must document in the source documents that the participant was given the Pregnant Partner Release of Information Form to provide to his partner.

8.4.5.2. Exposure During Breastfeeding

An EDB occurs if:

- A female participant is found to be breastfeeding while receiving or after discontinuing study intervention
- A female nonparticipant is found to be breastfeeding while being exposed or having been exposed to study intervention (ie, environmental exposure). An example of environmental EDB is a female family member or healthcare provider who reports that she is breastfeeding after having been exposed to the study intervention by ingestion, inhalation, or skin contact, etc.

The investigator must report EDB to Pfizer Safety within 24 hours of the investigator's awareness, irrespective of whether an SAE has occurred. The information must be reported using the CT SAE Report Form. When EDB occurs in the setting of environmental exposure, the exposure information does not pertain to the participant enrolled in the study, so the information is not recorded on a CRF. However, a copy of the completed CT SAE Report Form is maintained in the investigator site file.

An EDB report is not created when a Pfizer drug specifically approved for use in breastfeeding women (eg, vitamins) is administered in accordance with authorized use. However, if the infant experiences an SAE associated with such a drug, the SAE is reported together with the EDB.

8.4.5.3. Occupational Exposure

The investigator must report any instance of occupational exposure to Pfizer Safety within 24 hours of the investigator's awareness using the CT SAE Report Form, regardless of whether there is an associated SAE. Since the information about the occupational exposure does not pertain to a participant enrolled in the study, the information is not recorded on a CRF; however, a copy of the completed CT SAE Report Form must be maintained in the investigator site file.

8.4.6. Cardiovascular and Death Events

Not applicable.

8.4.7. Disease-Related Events and/or Disease-Related Outcomes Not Qualifying as AEs or SAEs

The following DREs are common in participants with IFD independent of exposure to study intervention, can be serious/life-threatening, and are defined as endpoints in this protocol:

- Death;

Because this event is typically associated with the disease under study, it will not be reported according to the standard process for expedited reporting of SAEs even though the event may meet the definition of an SAE. This event will be recorded on the corresponding CRF page in the participant's CRF within 24 hours of being made aware of the event. These DREs will be monitored by a safety review team on a routine basis.

Note: However, if either of the following conditions applies, then the event must be recorded and reported as an SAE (instead of a DRE):

- The AE leading to death is, in the investigator's opinion, of greater intensity, frequency, or duration than expected for the individual participant

OR

- The investigator considers that there is a reasonable possibility that the death was related to study intervention.

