
 To observe the additional safety and tolerability profile of isavuconazole. 	Other secondary safety endpoints: 
 Other AE summaries, including TEAE related to study intervention, Treatment-Emergent SAEs, TEAE leading to discontinuation of study intervention, TEAE leading to deaths, and all deaths. Other safety variables, including clinical laboratory variables, vital signs, 12-lead ECG and eye examination. 	
 Not applicable Not applicable

Objectives	Endpoints	Estimands

 To evaluate the PK of isavuconazole in the Chinese population with IFD caused by Aspergillus species and other filamentous fungi. 	
 Isavuconazole plasma concentrations at Day 3, 7, 14 and EOT visit. 	
 Not applicable
Exploratory	Exploratory	Exploratory

 To describe the efficacy of isavuconazole in the treatment of Chinese participants with IM. 	
 The percentage of all-cause mortality on Day 42 and 84 following primary treatment with isavuconazole. The crude rate of overall response at EOT, Day 42, and 84; and the crude success rates of the clinical, mycological, radiological responses based on the investigators' assessment at EOT, Day 42, and 84. 	
 The percentage of all-cause mortality on Day 42 and 84 will be estimated in participants with IM without regard to adherence to the isavuconazole treatment. The crude rate of overall response, clinical response, mycological response and radiological response at EOT, Day 42, and Day 84 will be estimated in participants with IM while participants are on the isavuconazole treatment. Data collected after use of the prohibited medications will not be used. Participants who are not available for clinical, mycological or radiological responses will be considered as a failure for overall response.
CCI		

If the investigator judges an SAE to have a causal relationship with the IMP, the investigator must additionally report the event to Pfizer Safety as described in [Section 10.3.3](#), Adverse Event Reporting section, even if that event is a component of the endpoint.

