8.2.7. Survival Status

Survival status will be recorded until the Follow-up visit and be evaluated through EOT in all participants, irrespective of when treatment was discontinued. Detailed requirement should be performed as specified in [Section 1.3 SoA](#).

If the participant has died, the date and cause of death along with the reporting of SAE details will be recorded in the eCRF.

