8.4. Adverse Events, Serious Adverse Events, and Other Safety Reporting

The definitions of an AE and an SAE can be found in [Appendix 3, Section 10.3](#).

AEs may arise from symptoms or other complaints reported to the investigator by the participant (or, when appropriate, by a caregiver, surrogate, or the participant's legally

authorized representative), or they may arise from clinical findings of the investigator or other healthcare providers (clinical signs, test results, etc.).

The investigator and any qualified designees are responsible for detecting, documenting, and recording events that meet the definition of an AE or SAE and remain responsible to pursue and obtain adequate information both to determine the outcome and to assess whether the event meets the criteria for classification as an SAE or caused the participant to discontinue the study intervention (see [Section 7.1](#)).

During the active collection period as described in [Section 8.4.1](#), each participant or legally authorized representative will be questioned about the occurrence of AEs in a nonleading manner.

In addition, the investigator may be requested by Pfizer Safety to obtain specific follow-up information in an expedited fashion.

Note: **Death** is considered an outcome of an AE. Whenever possible the underlying cause of death should be reported as the AE

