10.3.1. Definition of AE

AE Definition

• An AE is any untoward medical occurrence in a participant or clinical study participant, temporally associated with the use of study intervention, whether or not considered related to the study intervention.• Note: An AE can therefore be any unfavorable and unintended sign (including an abnormal laboratory finding), symptom, or disease (new or exacerbated) temporally associated with the use of study intervention.

Events Meeting the AE Definition

• Any abnormal laboratory test results (hematology, clinical chemistry, or urinalysis) or other safety assessments (eg, ECG, radiological scans, vital sign measurements), including those that worsen from baseline, considered clinically significant in the medical and scientific judgment of the investigator. Any abnormal laboratory test results that meet any of the conditions below must be recorded as an AE:
• Is associated with accompanying symptoms.• Requires additional diagnostic testing or medical/surgical intervention.• Leads to a change in study dosing (outside of any protocol-specified dose adjustments) or discontinuation from the study, significant additional concomitant drug treatment, or other therapy.• Exacerbation of a chronic or intermittent preexisting condition, including an increase in either frequency and/or intensity of the condition.• New condition detected or diagnosed after study intervention administration, even though it may have been present before the start of the study.• Signs, symptoms, or the clinical sequelae of a suspected drug-drug interaction.• Signs, symptoms, or the clinical sequelae of a suspected overdose of either study intervention or a concomitant medication. Overdose per se will not be reported as an AE or SAE unless it is an intentional overdose taken with possible suicidal/selfharming intent. Such overdoses should be reported regardless of sequelae.

Events **NOT** Meeting the AE Definition

- Any clinically significant abnormal laboratory findings or other abnormal safety assessments that are associated with the underlying disease, unless judged by the investigator to be more severe than expected for the participant's condition.
- The disease/disorder being studied or expected progression, signs, or symptoms of the disease/disorder being studied, unless more severe than expected for the participant's condition.

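### A death from expected progression of the fungal disease can be coded as no AE or as a fatal serious TEAE, depending on which protocol section a site follows, and the SAP does not settle it

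*Protocol*

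**What the plan says.** - **Protocol 8.4.7** has a heading that places its events outside AEs and SAEs, and it lists death as the only DRE. Of such a death it says "it will not be reported according to the standard process for expedited reporting of SAEs"; the death goes on a dedicated CRF page within 24 hours. There are two exceptions: the AE leading to death exceeded what was expected for that participant, or a relation to study drug is reasonably possible. In either case, "then the event must be recorded and reported as an SAE (instead of a DRE".
- **Protocol 10.3.1** lists among the things that are not AEs: "The disease/disorder being studied or expected progression, signs, or symptoms of the disease/disorder being studied, unless more severe than expected".
- **Protocol 8.2.7**: "If the participant has died, the date and cause of death along with the reporting of SAE details will be recorded in the eCRF". No DRE exception is given.
- **Protocol 8.4** treats death as the outcome of an AE: "Whenever possible the underlying cause of death should be reported as the AE". Again there is no DRE exception.
- **Protocol 8.4.1.1** sends "All SAEs occurring in a participant during the active collection period" to the sponsor's safety unit within 24 hours, and 10.3.2 counts an untoward occurrence that results in death as serious.
- **Protocol 3** makes TEAE incidence by SOC and PT the primary endpoint. The secondary safety endpoints include treatment-emergent SAEs and "TEAE leading to discontinuation of study intervention, TEAE leading to deaths, and all deaths".
- **SAP 6.6.1** plans tables of TEAEs, treatment-emergent SAEs and TEAEs leading to death, each for all causality and for treatment-related events, plus a listing of SAEs and deaths. The SAP text available for this review does not mention DREs.

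**The concern.** Take a participant who dies on Day 10 of progressive aspergillosis, judged unrelated to drug and no worse than expected. A site that follows 8.4.7 with 10.3.1 completes the DRE page and enters no AE. A site that follows 8.2.7 with 8.4 enters the progression as a fatal serious AE. Both sites comply with the protocol.

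The choice decides whether the event appears in three all-causality outputs: the primary TEAE table by SOC and PT, the treatment-emergent SAE table and the fatal TEAE table. The study is single-arm and open-label, so no control group would show a shift caused by coding practice. Expectedness and relatedness are both the investigator's judgement, and 10.1.5.1 provides no external data monitoring committee. All-causality counts are the natural check on those judgements, which is why they should not depend on the section a site happened to read.

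**Working it through.** **Step 1. The sections side by side, by type of death within the TEAE window**

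| Type of death | 8.4.7 | 10.3.1 | 8.2.7 | 8.4 | Conflict? |
|---|---|---|---|---|---|
| Possibly drug-related | SAE | AE | SAE details | Cause is the AE | No |
| AE leading to death worse than expected | SAE | AE | SAE details | Cause is the AE | No |
| Unrelated, not worse than expected, cause other than the fungal disease (e.g. bacterial sepsis) | Death is a DRE | Cause not excluded as the disease under study | SAE details | Cause is the AE | Mostly no: the cause can still be an AE |
| Unrelated, expected progression of the fungal disease | Death is a DRE | Not an AE | SAE details | Cause is the AE | **Yes** |

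The conflict is confined to the last row. Where causality is unknown, 10.3.3 handles the event as related for reporting purposes, which moves such deaths towards the first row.

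**Step 2. The denominator**

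The plan gives no figure for this point. Its one sizing figure (Protocol 9.5) fixes the denominator at 66 treated, and it reproduces: 1 − 0.97^66 = 0.866, the stated 86.6%.

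**Step 3. How many deaths**

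Inputs are Day 42 all-cause mortality on isavuconazole of 19% in the global Phase 3 aspergillosis study (Protocol 2.2.4) and 10% (1/10) in its Chinese subgroup (Protocol 2.1).

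- 66 × 0.10 = 6.6, about 7 deaths
- 66 × 0.19 = 12.54, about 13 deaths

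**Step 4. How far the fatal TEAE count can move**

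The documents do not give the share of deaths that would be recorded only as DREs. It is treated as an assumption *f* from 0 to 1. Fatal TEAEs = 13 × (1 − *f*), with exact (Clopper-Pearson) 95% intervals:

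| *f* | Fatal TEAEs of 66 | % | 95% CI |
|---|---|---|---|
| 0 | 13 | 19.7 | 10.9 to 31.3 |
| 0.25 | 10 (9.75) | 15.2 | 7.5 to 26.1 |
| 0.50 | 6 (6.5, rounded down) | 9.1 | 3.4 to 18.7 |
| 0.75 | 3 (3.25) | 4.5 | 0.9 to 12.7 |
| 1 | 0 | 0 | 0 to 5.4 |

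With 7 deaths the range is 7/66 (10.6%) to 0/66. The serious TEAE count moves by up to the same number, less any participant who has another SAE.

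**The case against.** The best reply is that the sections can be read together: the fact of death is the DRE, and its cause is an AE. There is real support for this. The operative sentence in 8.4.7 lifts only the expedited process, and its first exception presupposes that some AE led to the death. The Amendment 1 rationale in Appendix 10 says that the cause of death should be reported as an AE. Section 8.4.8.1 also requires investigators to report the clinical consequences of lack of efficacy, although it does not name the AE page.

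This establishes the likely intent, but it does not remove the conflict. The current 8.4.7 does not state the intent, and its heading and exception wording point the other way. Where the cause is expected fungal progression, 10.3.1 says that there is no AE to enter.

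Other parts of the reply stand and limit the point:

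- The rule in 8.4.1.1 is general and 8.4.7 is a specific exemption from it. That pair alone is not a contradiction.
- A reader might infer that deaths to which the drug contributed drop out of the safety tables. The documents do not support that. Section 8.4.7 makes any death with a reasonable possibility of relation an SAE, and 10.3.3 handles unknown causality as related for reporting. Only a misattributed death could be lost, and misattribution is a risk in any open-label study.
- Deaths remain visible. All deaths is a named endpoint, Day 42 and Day 84 mortality are analysed separately, and SAP 6.6.1 lists deaths. None of these gives fatal events by SOC and PT, however, and under SAP 5.3 crude mortality also counts some participants with unknown survival status as dead.

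**Conclusion.** For deaths from expected progression of the fungal disease, 8.4.7 with 10.3.1 conflicts with 8.2.7 and 8.4, and the SAP does not say how DRE deaths are tabulated. The all-causality TEAE, treatment-emergent SAE and fatal TEAE counts can therefore depend on which section a site follows. Treatment-related tables, deaths from other reportable causes and total mortality are largely unaffected.

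About 7 to 13 deaths by Day 42 are plausible. With 13, the fatal TEAE count could lie anywhere from 0 to 13 of 66. A reader might take 0% against 19.7% as the likely error. It is only an outer bound: the zero end requires every death to be expected fungal progression and every site to take the same reading, while the mortality inputs are all-cause in patients with serious underlying disease.

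The range also assumes that mortality from the earlier study carries over, that all Day 42 deaths fall within 28 days of last dose, and that no deaths after Day 42 are added. The issue deserves correction because the stated rules conflict on declared safety endpoints.

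**What to change.** **Protocol.** State in 8.4.7 that the DRE provision waives only expedited SAE reporting. State also that the underlying cause of every death from first dose to 28 days after last dose, including progression of the fungal disease, is entered on the AE page with outcome fatal. Cross-reference this in 10.3.1, as an exception to the exclusion of expected progression, and in 8.2.7.

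**SAP 6.6.1.** State that these events count in the all-causality serious and fatal TEAE tables. Show deaths recorded as DREs on a separate line by investigator attribution, so that the counts can be read with and without them.

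**Cost.** The text is a few sentences, and date and cause of death are already collected under 8.2.7. The change still needs a protocol amendment with ethics approval, and health authority approval if it is classed as substantial (10.1.1). It also needs CRF guidance and some data entry for participants already enrolled. Fatal and serious TEAE rates will look less favourable, which the separate line makes interpretable. Relief from expedited reporting is kept.
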